9.1.2 TEZ/IVA Run-in Period (Part 2)

The TEZ/IVA Run-in Period of Part 2 is 4 weeks. Subjects will be evaluated as outpatients.

Study visits during the Run-in Period will occur as shown in [Table 3-2](#). Study drug administration details are provided in [Section 9.6](#).

On the Day -14 Visit, spirometry and sweat chloride will be assessed. The Day -14 Visit spirometry assessment will be used for stratification of randomization ([Section 9.2](#)).

Study eligibility will be confirmed before the first dose of TEZ/IVA in the Run-in Period (on the Day -28 Visit). Subjects who prematurely discontinue TEZ/IVA during the Run-in Period will not be randomized or participate in the Treatment Period, unless they rescreen and complete another 4-week Run-in Period ([Section 9.1.1.2](#)).

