9.2 Method of Assigning Subjects to Treatment Groups

A randomization list for each part will be produced by Vertex Biostatistics or a qualified randomization vendor. The Vertex study biostatistician will review and approve the dummy randomization list. The final randomization list will be reviewed and approved by a designated unblinded biostatistician who is not a member of the study execution team (SET).

Subjects will be assigned a unique subject number. Only subjects who have completed screening assessments and are eligible for participation in the study (and completed the Run-in Period and qualify to enter the Treatment Period [Part 2]) will be randomized to receive active study drug or placebo or active control during the Treatment Period.

Randomization will be stratified by ppFEV₁ determined during screening (Day -28 to Day -1 assessment; <70 versus ≥70) in Parts 1 [REDACTED] and the TEZ/IVA Run-in Period (Day -14 assessment; <70 versus ≥70) in Part 2. If the Day -14 ppFEV₁ value is not valid or not available, the most recent available ppFEV₁ value before the date of randomization will be used for stratification.

An interactive web response system (IWRS) will be used to assign subjects to treatment.

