9.3 Rationale for Study Elements

9.3.1 Study Design

Parts 1 [REDACTED]

Parts 1 [REDACTED] will evaluate the safety, tolerability, PK, PD, and efficacy of VX-121 administered in TC with TEZ/VX-561 (Part 1) [REDACTED] in subjects with CF with F/MF genotypes.

Efficacy has not been established for a corrector, potentiator, or any corrector/potentiator combination in subjects with F/MF genotypes. Because there is no effective treatment for this population, a placebo arm will be included as the control treatment to assess whether any observed effects are treatment-related or simply related to the study conditions.

The Washout Period (18 ± 3 days; Section 9.1.4) is included to enable a more thorough evaluation of VX-121 exposure-response relationships by conducting PK and PD assessments during the VX-121 washout.

Part 2

Part 2 will evaluate the safety, tolerability, PK, PD, and efficacy of VX-121 in TC with TEZ/VX-561 in subjects with CF with the F/F genotype, if the sponsor chooses to conduct this optional part of the study.

The efficacy and safety of TEZ/IVA in F/F subjects have been demonstrated in Study VX14-661-106 (Study 661-106).¹² Therefore, placebo/TEZ/IVA has been chosen as the control treatment to assess whether any observed effects are treatment-related or simply related to the study conditions.

A 4-week TEZ/IVA Run-in Period (Section 9.1.2) is included to establish a reliable on-treatment (TEZ/IVA) baseline for the Treatment Period.

The 4-week Washout Period (Section 9.1.4) is included to evaluate the effect on PD and efficacy endpoints as subjects step down from TC to TEZ/IVA, after the VX-121 washout.

Parts 1, 2, [REDACTED]

The extent of response to CFTR modulator treatment may depend on the subject's ppFEV₁ value (an index of disease severity) before the start of TC study drug dosing. Some subjects in Part 2 (subjects with the F/F genotype) may be receiving treatment with LUM/IVA or TEZ/IVA at screening, while some subjects may not be receiving treatment with CFTR modulators. It is unlikely that subjects enrolling in Parts 1 [REDACTED] (subjects with F/MF genotypes) are receiving LUM/IVA or TEZ/IVA at screening, as the benefit of these drugs has not been established in patients with F/MF genotypes. Therefore, randomization will be stratified by the ppFEV₁ value determined during screening for Parts 1 [REDACTED] and during the TEZ/IVA Run-in Period, after at least 13 days of TEZ/IVA (Day -14 assessment), in Part 2.

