12.3.1 General Considerations

Continuous variables will be summarized using the following descriptive summary statistics: the number of subjects (n), mean, SD, median, minimum value, and maximum value. Categorical variables will be summarized using counts and percentages.

All individual subject data for subjects who were randomized or received at least 1 dose of study drug will be presented in individual subject data listings.

The baseline value, unless otherwise specified, will be defined as the most recent non-missing measurement (scheduled or unscheduled) collected before the first dose of study drug in the Treatment Period. For ECG, baseline will be defined as the most recent pretreatment measurement (or the average of triplicate measurements, if the most recent pretreatment measurement is obtained in triplicate) before the first dose of study drug. Further details on baseline definition will be provided in SAP.

Absolute change from baseline will be calculated as post-baseline value – baseline value.

The **Treatment-Emergent (TE) Period** will be from first dose date of TC to 28 days after the last dose date of study drug, or the completion date of study participation, whichever comes earlier. An additional TE Period related to the Run-in Period for Part 2 will be defined in the SAP, as appropriate.

The rules for handling missing data due to treatment or study discontinuation will be described in the SAP.

All data will be summarized for each part, separately, unless specified otherwise.

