**Figure 6-2 VX18-121-101 Study Design for Part 2 (F/F Genotype)**

	Run-in Period a,b (4 weeks)	Treatment Period b,c (4 weeks)	Washout Period b (4 weeks)	
Screening Period (4 weeks)	TEZ/IVA	TC-20 mg (VX-121/TEZ/VX-561) N = 18	TEZ/IVA	Safety Follow-up Period (4 weeks)
		Pbo + TEZ/IVA N = 9		

FDC: fixed-dose combination; F/F: *F508del/F508del*; IVA: ivacaftor; N: number of subjects; Pbo: placebo; ppFEV1: percent predicted forced expiratory volume in 1 second; q12h: every 12 hours; qd: daily; TC: triple combination; TEZ: tezacaftor

Note: Randomization will be stratified by ppFEV1.

a All subjects are required to complete the TEZ/IVA Run-in Period to establish a reliable on-treatment (TEZ/IVA) baseline.

b The dosage of TEZ/IVA will be TEZ 100 mg qd/IVA 150 mg q12h, which will be administered as TEZ 100 mg/IVA 150 mg FDC in the morning and IVA 150 mg in the evening.

c Part 2 will evaluate the same VX-121 dose (20 mg qd) used in Part 1. The dosage of TEZ and VX-561 will be TEZ 100 mg qd and VX-561 150 mg qd.

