## 6.3 Randomization

Only subjects who have completed screening assessments and are eligible for participation in the study (and completed the Run-in Period and qualify to enter the Treatment Period [Part 2]) will be randomized to receive active study drug or placebo or active control during the Treatment Period.

Randomization will be stratified by ppFEV1 determined during screening (Day -28 to Day -1 assessment; <70 versus ≥70) in Parts 1 [REDACTED] and the TEZ/IVA Run-in Period (Day -14 assessment; <70 versus ≥70) in Part 2. If the Day -14 ppFEV1 value is not valid or not available, the most recent available ppFEV1 value before the date of randomization will be used for stratification.

An interactive web response system (IWRS) will be used to assign subjects to treatment.

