- The TE period for the Treatment Period will include the time from the first dose of study drug in the Treatment Period to 28 days after the last dose of study drug (from treatment period or washout period) or the completion date of study participation (obtained from the end of follow-up page of the CRF), whichever occurs first.

**Baseline value**, unless otherwise specified, will be defined as the most recent non-missing measurement (scheduled or unscheduled) collected before the first dose of study drug in the Treatment Period. For ECG, baseline will be defined as the most recent non-missing measurement (or the average of triplicate measurements, if the most recent non-missing measurement is obtained in triplicate), before the first dose of study drug in the Treatment Period.

**Absolute change** from baseline will be calculated as postbaseline value – baseline value.

**Relative change** from baseline will be calculated as (postbaseline value – baseline value)/baseline value.

**Unscheduled visits:** Unscheduled visit measurements will be included in analysis as follows:

- In scheduled visit windows per specified visit windowing rules
- In the derivation of baseline
- In the derivation of maximum and minimum values during TE period, and maximum and minimum change from baseline values for safety analyses
- In individual subject data listings as appropriate

**Visit windowing rules:** The analysis visit windows for protocol-defined visits are provided in [Appendix A](#).

Spirometry (ppFEV1) will be used for both efficacy and safety purposes. For efficacy analysis, the assessments will follow the visit windowing rules for efficacy. For safety analysis, the nominal visits will be used for ppFEV1 collected at both pre-dose on Day 1 and pre-dose on Day 2 (for Part 1 only).

**Incomplete/missing data** will not be imputed, unless specified otherwise.

**Outliers:** No formal statistical analyses will be performed to detect or remedy the presence of statistical outliers.

**Multiplicity:** There will be no multiplicity adjustment for performing multiple hypothesis tests.

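### The Part 2 baseline rule has no earliest date, so in an uncommon case a value from before the TEZ/IVA Run-in can serve as baseline

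*SAP*

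**What the plan says.** SAP 8.1 uses one baseline rule for all parts: the "most recent non-missing measurement (scheduled or unscheduled) collected before the first dose of study drug in the Treatment Period". ECG has a variant for triplicate readings. SAP Appendix A, Table 11-1 repeats the rule for Part 2 as a window that ends at Day 1 predose and has no start. Protocol 12.3.1 gives the same rule and adds that "Further details on baseline definition will be provided in SAP". The details the SAP adds are the ECG averaging rule and an allowance for sweat collections that end up to 30 minutes after the first dose. Neither is specific to Part 2.

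The purpose of the Part 2 baseline is stated in SAP Figure 6-2, footnote a: "All subjects are required to complete the TEZ/IVA Run-in Period to establish a reliable on-treatment (TEZ/IVA) baseline". Protocol 9.1.2 provides one Run-in assessment of the two main measures: "On the Day -14 Visit, spirometry and sweat chloride will be assessed". The conditions for entering the Treatment Period (Protocol 9.1.3) concern clinical stability and do not require a valid Day -14 or Day 1 measurement.

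Protocol 9.2 and SAP 6.3 foresee a lost Day -14 value, for stratification only: "If the Day -14 ppFEV₁ value is not valid or not available, the most recent available ppFEV₁ value before the date of randomization" is then used. That fallback also carries no on-treatment condition.

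**The concern.** Change from baseline in Part 2 is meant to measure the move from TEZ/IVA to the triple combination. If baseline predates the Run-in, the change also contains whatever TEZ/IVA did. Protocol 9.3.1 says that TEZ/IVA efficacy in F/F subjects has been demonstrated, so the expected direction is to inflate the apparent gain in the triple-combination arm and to show a gain in the TEZ/IVA control arm that did not arise in the Treatment Period.

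The primary ppFEV₁ test is within-group (Protocol 12.3.4.1, SAP 8.3.1.2), so a comparison with control does not remove this. SAP 8.3.1.4 plans no sensitivity analysis, and no planned output identifies subjects with such a baseline. A Screening ppFEV₁ may also be post-bronchodilator (Protocol 11.5.1), which adds a second difference in measuring conditions.

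**Working it through.** **Step 1. Which value does the rule return?** Protocol Table 3-2 (assessments are predose unless noted) gives:

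| Measure | Scheduled before the first Treatment Period dose | What must fail to reach a pre-Run-in value |
|---|---|---|
| ppFEV₁, sweat chloride | Screening, Day -14, Day 1 | Day 1 and Day -14, with no unscheduled Run-in value |
| Chemistry, hematology, coagulation, ECG, vital signs | Screening, Day -28, Day 1 | Day 1 alone, with no unscheduled Run-in value |
| CFQ-R | Day 1 | Not applicable: baseline would be missing |

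A Day -14 value is on treatment: Protocol 9.3.1 places it "after at least 13 days of TEZ/IVA (Day -14 assessment), in Part 2".

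**Step 2. The plan's own figure.** SAP 6.2 states at least 90% power with n = 18, a within-group change of 7 and SD 8. A one-sample t-test at two-sided 5% has noncentrality (7/8) × √18 = 3.71 and power 93.8%. The stated figure is reproduced, and the baseline question does not alter it.

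**Step 3. Shift per affected subject.** If k subjects in an arm of n have a pre-TEZ/IVA baseline and their TEZ/IVA effect is d, the unadjusted arm mean moves by k × d / n. This ignores the baseline covariate in the MMRM. The documents give no d, so the ranges are assumptions.

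- ppFEV₁, d = 2 to 6 points, k = 1: 2/18 = 0.11 to 6/18 = 0.33 in the triple-combination arm; 2/9 = 0.22 to 6/9 = 0.67 in control.
- Standard errors at SD 8: 8/√18 = 1.89 and 8/√9 = 2.67.
- Against the 7-point planning effect, 0.11 to 0.33 is 1.6% to 4.8%.
- Sweat chloride, d = 5 to 15 mmol/L, k = 1: 5/18 = 0.28 to 15/18 = 0.83; 5/9 = 0.56 to 15/9 = 1.67.

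**Step 4. Effect on the within-group test.** The probability of rejecting at two-sided 5% when the true change is zero (noncentral t, SD 8, d = 2 to 6) is:

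| Affected subjects | n = 18 | n = 9 |
|---|---|---|
| 1 | 5.04% to 5.3% | 5.06% to 5.6% |
| 3 | 5.3% to 7.9% | 5.6% to 10.2% |

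**Step 5. How often.** The documents give no missing-visit rate. Assume 2% to 10% per visit.

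- Efficacy, both visits lost independently: 27 × 0.02² = 0.01 to 27 × 0.10² = 0.27 subjects expected. The chance of at least one is 1 − (1 − 0.0004)²⁷ = 1% to 1 − (1 − 0.01)²⁷ = 24%. If losses cluster in the same subjects, the count rises, with the single-visit figure below as its ceiling.
- Safety, Day 1 lost: 27 × 0.02 = 0.54 to 27 × 0.10 = 2.7 subjects expected. The chance of at least one is 1 − 0.98²⁷ = 42% to 1 − 0.90²⁷ = 94%.

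**The case against.** The strongest reply is that the efficacy case is remote. Day 1 predose is the ordinary baseline, and the first dose is given at the site after the predose assessments (Protocol 9.6). The Day -14 Visit has a +13-day window. Sweat is collected from both arms and one valid arm suffices (SAP 8.3.2.1). The 30-minute allowance rescues late collections, and unscheduled Run-in values count. The effect also shrinks or vanishes in subjects already on a modulator: "Some subjects in Part 2 (subjects with the F/F genotype) may be receiving treatment with LUM/IVA or TEZ/IVA at screening". All of this stands, and it is why the expected effect is small.

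For safety, the analysis is descriptive (SAP 8.4), and many Appendix E criteria, such as multiples of ULN, do not use baseline. Scheduled Day 1 laboratory, ECG and vital-sign values of uncertain timing are treated as predose (Table 11-1, note 3). These points also stand, but change-from-baseline and shift summaries still depend on the rule.

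A reader might infer that the rule contradicts the purpose of the Run-in, or that Part 2 changes in general include a TEZ/IVA effect. The documents do not support either reading. The rule is anchored to the first Treatment Period dose after a required Run-in, and it returns an on-treatment value whenever the Day 1 or Day -14 value exists. Nor does the stratification fallback show that a double loss is expected, since it concerns Day -14 alone. What remains is an unaddressed case.

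**Conclusion.** The gap is real and minor. Nothing in the baseline rule, its analysis window or the Treatment Period entry conditions keeps a pre-Run-in value out of the Part 2 baseline. For ppFEV₁ and sweat chloride this needs two lost visits and no unscheduled Run-in value; for laboratory, ECG and vital-sign data it needs one lost Day 1 value.

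Under the assumed 2 to 6 point TEZ/IVA effect, one affected subject shifts a ppFEV₁ arm mean by well under half a standard error in either arm, and the test's error rate barely moves. Between-group contrasts are distorted only if affected subjects are unevenly spread; the within-group primary analysis lacks that protection. The sizes rest on assumed effects and the frequencies on assumed missingness. That the rule permits the case rests on the text alone.

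**What to change.** In SAP 8.1 and Table 11-1, for Part 2 only:

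- **ppFEV₁ and sweat chloride.** Define baseline as the latest valid value, scheduled or unscheduled, collected on Run-in TEZ/IVA, from the Day -14 Visit or after a comparable time on TEZ/IVA (at least 13 days), up to the first Treatment Period dose. Keep the 30-minute sweat chloride allowance. If no such value exists, treat baseline as missing for that endpoint and report how many subjects this affects.
- **Laboratory, ECG and vital signs.** Keep the existing baseline, but flag, count and list subjects whose baseline predates the first Run-in dose. Setting these baselines to missing would remove subjects from change and shift tables in arms of 18 and 9, which is a debatable trade for descriptive data.

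Leave Part 1 unchanged.

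The cost is a sentence or two of SAP text, one date condition and one flag in the programming. A dosed subject with no on-treatment value leaves that endpoint's change analysis; this is likely to be at most about one subject. Power for 7 points at SD 8 would be 92.3% with n = 17 and 90.5% with n = 16, so the 90% statement survives the loss of two triple-combination subjects. It falls to 88.3% at n = 15.

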## 8.2 Background Characteristics

### 8.2.1 Subject Disposition

The number of subjects in the following categories will be presented by treatment group and overall for Parts 1 ██████:

- All Subjects Set;
- Randomized;
- Safety Set;
- Full Analysis Set;
- Randomized but not dosed.

The number of subjects for the Treatment Period in the following categories will be presented by treatment group and overall for Part 2:

- Randomized or dosed in the Treatment Period;
- Randomized;
- Safety Set for the Treatment Period;
- Full Analysis Set;
- Randomized but not dosed in the Treatment Period.

The number and percentage (based on FAS) of subjects in each of the following disposition categories will be presented by treatment group and overall:

- Completed study drug treatment (Separated by Treatment Period and Washout Period for all parts);
- Prematurely discontinued treatment and the reason for discontinuation (i.e., discontinued all study drugs) (Separated by Treatment Period and Washout Period for all parts);
- Completed study (i.e., completed Safety Follow-up Visit);
- Prematurely discontinued the study and the reason for discontinuation.

A separate disposition table will be provided for the Run-in Period in Part 2 with the following categories:

- All Subjects Set
- Safety Set for the Run-in Period

The number and percentage (based on Safety Set for the Run-in Period) of subjects in each of the following disposition categories will be presented:

- Completed treatment in the Run-in Period;
- Prematurely discontinued treatment during run-in and the reason for treatment discontinuation;
- Prematurely discontinued study during run-in and the reason for study discontinuation.

A listing will be provided by part, for subjects who discontinued treatment (including the Run-in Period in Part 2) or who discontinued study with reasons for discontinuation.

### **8.2.2 Demographics and Baseline Characteristics**

Demographics and baseline characteristics will be summarized based on the FAS, and presented by treatment group and overall, for each part.

Demographic data will include the following:

- Age at baseline (in years)
- Sex (female or male)
- Ethnicity (Hispanic or Latino, not Hispanic or Latino, and not collected per local regulations)
- Race (White, Black or African American, Asian, American Indian or Alaska Native, Native Hawaiian or Other Pacific Islander, Other, and not collected per local regulations)

Baseline characteristics will include the following:

- Weight (kg)
- Height (cm)
- BMI (kg/m^2)

Stratification categories will include the following:

- ppFEV1 at stratification (< 70 and ≥ 70)

For Parts 1 [REDACTED] ppFEV1 stratification (<70 versus ≥70) will be performed using the screening ppFEV1 value.

For Part 2, ppFEV1 stratification (<70 versus ≥70) will be performed using the value obtained at Day -14 Visit

Disease characteristics will include the following:

- ppFEV1 at baseline (<40, ≥ 40 to <70, ≥70 to ≤90, >90)
- ppFEV1 at baseline (continuous)
- Sweat Chloride at baseline (continuous)
- FEV1 (L) at baseline (continuous)
- CFQ-R respiratory domain score at baseline (continuous)
- Prior use of dornase alfa before first dose of study drug in the Treatment Period (Yes, No)
- Prior use of azithromycin before first dose of study drug in the Treatment Period (Yes, No)
- Prior use of inhaled antibiotic before first dose of study drug in the Treatment Period (Yes, No)
- Prior use of inhaled bronchodilator before first dose of study drug in the Treatment Period (Yes, No)
- Prior use of inhaled hypertonic saline before first dose of study drug in the Treatment Period (Yes, No)
- Prior use of inhaled corticosteroids before first dose of study drug in the Treatment Period (Yes, No)
- Infection with *Pseudomonas aeruginosa* within 2 years prior to screening (Positive, Negative)

In addition, data listings will also be provided for:

- Informed consent;
- Inclusion/Exclusion criteria violation for subjects with any such violations.

### 8.2.3 Medical History

Medical history will be coded by using the Medical Dictionary for Regulatory Activities (MedDRA). For the FAS, medical history will be summarized descriptively by system organ class and preferred term. The corresponding data listing will also be provided.

In addition, the number of subjects reported to have had positive cultures for respiratory pathogens within the 2 years prior to screening (i.e., answered yes on the respiratory microbiology form) will be summarized for the FAS. The corresponding data listing will be provided.

## 8.2.4 Prior and Concomitant Medications

Medications will be coded using the World Health Organization Drug Dictionary (WHO-DD) and categorized as follows:

For Parts 1 [REDACTED]:

**Prior medication:** any medication that started before the first dose date of study drug.

**Concomitant medication:** medication continued or newly received during the TE period.

**Post-treatment medication:** medication continued or newly received after the TE period.

A given medication may be classified as follows: prior, concomitant, post-treatment, both prior and concomitant, both concomitant and post-treatment, or prior, concomitant, and post-treatment.

For Part 2:

**Prior medication:** any medication started before the first dose of study drug in the Run-in Period.

**Concomitant medication during the Run-in Period:** medication continued or newly received during the TE period for the Run-in Period.

**Concomitant medication during the Treatment Period:** medication continued or newly received during the TE period for the Treatment Period.

**Post-treatment medication:** medication continued or newly received after:

- the TE period for the Run-in Period for subjects who did not receive study drug in the Treatment period,  
or
- the TE period for the Treatment Period for the subjects who received study drug in the Treatment Period.

A given medication may be classified as any combination of the above categories, for example, prior and concomitant during the Run-in Period, concomitant during the Treatment Period and post-treatment, or concomitant during Run-in period, concomitant during Treatment Period, and post-treatment.

If a medication has completely missing or partially missing start/stop date and it cannot be determined whether it was taken before the first dose date of study drug, concomitantly, or after the TE period, it will be classified as prior, concomitant, and post-treatment.

For the FAS in Parts 1 [REDACTED] prior medications and concomitant medications will be summarized descriptively by 1) treatment group and overall, preferred name (PN); and 2) treatment group and overall, anatomic class (ATC) level 1, ATC level 2, and PN.

Prior and concomitant medication during the Run-in Period will be summarized together in one summary table for the FAS in Part 2 by treatment group. The concomitant medications during the treatment period will be summarized descriptively for Part 2 in the same way as for Part 1 [REDACTED] by treatment group for FAS.

Post-treatment medications will be listed for each subject. Details for imputing missing or partial start and/or stop dates of medication are described in [Appendix B](#).

